##### ***10.1.10.1 Primary efficacy endpoint***

###### ***Primary analysis of the primary endpoint***

The primary efficacy endpoint will be the therapeutic cure at Visit 3 in the MITT-PA/SA population.

In order for the requirements of the combination policy to be satisfied, both comparisons of the combination to the components alone must show the combination to be statistically significantly better than the component alone using a two-sided 0.05 significance level.

The number and percentage of patients with therapeutic cure at Visit 3 will be summarized by treatment group. The proportion of patients with a therapeutic cure will be compared between the treatment groups by using a chi-squared test.

Efficacy analyses of the primary endpoint will also be conducted on the MITT, MPP, CITT and CPP populations.

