- Presumed Eradication if the culture does not show growth of any pathogen or if there is no material to culture and the Overall Clinical Outcome is Clinical Improvement or Clinical Cure as defined above;
- Presumed Persistence if the Overall Clinical Outcome is Clinical Failure but no culture result is available from Visit 4;
- Recurrence if there is no material to culture, the Overall Clinical Outcome is Clinical Failure, and the Overall Clinical Outcome at Visit 3 is Clinical Cure;
- Superinfection if a pathogen not present at Visit 1 and Visit 3 is now present;
- Indeterminate if none of the above definitions are met and the bacteriologic response cannot be determined.

The above rules will be used for microbiological outcome summaries for the patients in the CITT and CPP populations that have no pathogen at Visit 1, since microbiological response cannot be calculated without any pathogen at Visit 1.

If Overall Clinical Outcome at Visit 3 is Clinical Failure (whether or not the patient discontinues prematurely) and no bacterial culture is performed at Visit 3, the bacteriologic response at Visit 3 will be Presumed Persistence. If Overall Clinical Outcome at Visit 4 is Clinical Failure and no bacterial culture is performed at Visit 4, the bacteriologic response at Visit 4 will be Presumed Persistence.

Therapeutic cure: TSSS (otalgia+edema+otorrhea) of 0 and bacteriological response of eradication or presumed eradication

Therapeutic failure:

- Positive culture for pathogens (independent of TSSS) or
- Negative culture or presumed eradication with TSSS>0

If a patient took rescue medication prior to Visit 3, the response will be considered a failure at Visit 3. Similarly, if patient took rescue medication prior to Visit 4, the response will be considered a failure at Visit 4.

Therapeutic response will be summarized by treatment group and visit in terms of proportion of cures and failures at each visit.

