A Pearson's Chi Squared test for independence will be used to test the hypotheses states in Section 4.7.1 that there is no difference between the combined treatment and each individual component at Visits 3 and 4. If less than 80% of the expected counts are less than 5 or at least one category has no patients in a treatment group, then Fisher's exact test will be used. Differences in response rates with the corresponding 95% CIs will be reported. Sensitivity analyses to investigate the impact of the choice of method for handling missing data and the choice of analysis population will be performed as described in Section 4.7.1.3.

The homogeneity of the treatment effect for a number of important subgroups will be investigated as described in Section 4.7.1.4.

A by-patient listing of the therapeutic response will be provided.

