- Grade I: Tympanic membrane seen. Canal erythematous
- Grade II: Debris in ear canal. Tympanic membrane often obscured by debris.
- Grade III: Edematous ear canal. Tympanic membrane obscured by edematous ear canal. No systemic illness.
- Grade IV: Edematous ear canal. Perichondritis (pinna cellulitis). Systemic illness.

The number and percentage of patients with each grade will be summarized by visit and treatment group.

Grades will also be summarized in terms of a 3-level and a 2-level response. For the 3-level response, the proportion of patients with a Brighton grading of “0” will be considered as Resolved. It will be considered as “Improved” at Visit 3 and Visit 4 if the grade is lower than the previous visit. Brighton grading will be considered as “Not Improved” otherwise. Furthermore if Brighton grading is considered “Not Improved” or “Improved” in the 3-level response then it will be identified as “Not Resolved” in the 2-level response. If it is considered “Resolved” in the 3-level response then it will also be considered “Resolved” in the 2-level response.

If a patient took rescue medication prior to Visit 3, the response will be considered not resolved at Visit 3. Similarly, if a patient took rescue medication prior to Visit 4, the response will be considered not resolved at Visit 4.

For Visits 3 and 4, the proportion of patients with a response of Resolved and Not Resolved will be compared between the treatment groups by using the same chi-squared test as the primary efficacy endpoint.

A by-patient listing of Brighton grading data will be provided.

Otalgia

Effective Date: [REDACTED]

Related to: [REDACTED]

CONFIDENTIAL

Project Document Version No. 2.0
Project Document Effective Date: Date of last signature
Page 25 of 34

Otalgia will be assessed by the Investigator at Visits 1, 3, and 4. Otalgia will be assessed as Severe, Moderate, Mild, or Absent as defined in Section 4.7.2.

The number and percentage of patients with each outcome (Severe, Moderate, Mild or Absent) will be summarized by visit and treatment group.

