4.10 Determination of Sample Size

Planned enrollment is 500 children, adolescents and adults. Patients will be stratified at enrollment so that approximately 50% of those enrolled will be younger than 18 years old and approximately 50% will be over 18 years old or older. Stratification is being performed to ensure adequate representation of each age group in the study and not for statistical considerations.

We have not been able to find an accurate estimation of study's main variable (therapeutic cure) in previous investigations with Ciprofloxacin 0.3% otic solutions in the treatment of AOE. Rates of patients cured, with different definitions from ours, have been estimated within a range between 60% and 70%. Moreover, in two comparative trials testing the same combination (same product) versus Ciprofloxacin alone in the treatment of AOMT, the percentage of therapeutic cure in patients with *Pseudomonas aeruginosa* and *Staphylococcus aureus* was around 50%.

For the calculation of the sample size for this study, the assumption is made that the Ciprofloxacin alone group will have a therapeutic cure rate of 62%, and that the combination will increase it by a relative 25%, which would represent a therapeutic cure rate of 78%. Assuming a two-sided significance level of 5%, and a statistical power of 80%, the required number of patients in each group would be 150. The randomization schedule is defined as 2:2:1 (Ciprofloxacin plus Fluocinolone

acetonide:Ciprofloxacin:Fluocinolone acetonide), so the total number of evaluable patients to be recruited is 375 (150 : 150 : 75). It is expected that approximately 80% of enrolled patients will complete the study.

In this study, evaluable patients are those with a positive pathogen microbiological culture at baseline (MITT population). From previous studies in AOE, the rate of patients included with a negative culture at baseline is approximately 25%, and therefore the number of patients to be finally recruited to obtain 375 evaluable patients would be 500.

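### The SAP's rule for switching to Fisher's exact test is inverted, so read literally it replaces the declared primary chi-squared test at any realistic sample size

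*SAP*

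**What the plan says.** SAP 4.7.2 sets the main test for the primary endpoint: "A Pearson's Chi Squared test for independence will be used to test the hypotheses". It then gives the exception, "If less than 80% of the expected counts are less than 5 or at least one category has no patients in a treatment group", followed by "then Fisher's exact test will be used. Differences in response rates with the corresponding 95% CIs will be reported". SAP 4.5.3 repeats the same condition for comparing types of pain treatment.

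Protocol 10.1.10.1 has no exception: "The proportion of patients with a therapeutic cure will be compared between the treatment groups by using a chi-squared test". SAP 4.7.1 likewise names only a two-sided chi-square test at alpha 0.05. Most of the secondary endpoints in SAP 4.7.3 inherit the rule, because they "will be compared between the treatment groups by using the same chi-squared test as the primary efficacy endpoint". Nothing in either document corrects the direction of the condition.

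**The concern.** The usual safeguard drops chi-squared when too many expected counts are small, that is, when fewer than 80% of them are 5 or more. The SAP instead drops it when fewer than 80% of them are below 5. That removes chi-squared where its approximation is sound and keeps it only where the approximation is poor.

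A programmer who follows SAP 4.7.2 literally reports Fisher. One who follows SAP 4.7.1 and Protocol 10.1.10.1 reports chi-squared. The two tests can fall on opposite sides of 0.05. Because the combination must beat both components, a reversal in either comparison decides the trial.

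**Working it through.** **Inputs from the documents.** Two-sided alpha 5%, power 80%, ciprofloxacin cure rate 62%, relative increase 25% (62% × 1.25 = 77.5%, stated as 78%), and 150:150:75 evaluable patients (SAP 4.10). The outcome is cure or failure (SAP 4.7.2), so each comparison is a 2x2 table.

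**Assumptions.** The documents give no cure rate for fluocinolone alone; 40% to 62% is used. They do not give the size of the MITT-PA/SA population either. The 150 per arm in SAP 4.10 counts patients with any pathogen (MITT), while the primary analysis uses the narrower *P. aeruginosa*/*S. aureus* subset, so 120 and 90 per arm are shown as illustrations.

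**1. The plan's own sample size.** With p̄ = 0.6975 and d = 0.155:

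n = [1.96·√(2·0.6975·0.3025) + 0.8416·√(0.62·0.38 + 0.775·0.225)]² / 0.155² = 136.7

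With continuity correction: (136.7/4)·[1 + √(1 + 4/(136.7·0.155))]² = 149.3, so 150. This matches the stated figure. The uncorrected formula gives 137; at 78% the results are 128 uncorrected and 140 corrected.

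**2. What the condition does.** Four cells allow only five shares of expected counts below 5: 0, 25, 50, 75 or 100%. The first four are all under 80% and select Fisher. Chi-squared survives only at 100%, and then only if no category is empty. The four expected counts sum to the two-arm total, so all being below 5 requires a total under 20. A search over whole-number margins gives at most 18 patients, or 12 with 2:1 allocation.

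**3. Expected counts at the planned sizes** (expected count = row total × column total / N).

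| Comparison | Expected cures / failures per arm | Share below 5 |
|---|---|---|
| 150 v 150, 78% v 62% | 105 / 45 in each arm | 0% |
| 150 v 75, 78% v assumed 50% | 103 / 47 and 51.5 / 23.5 | 0% |

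Since 0% is less than 80%, Fisher is selected. Summing binomial probabilities over all possible tables, the literal rule selects Fisher with probability 1.000. With the direction corrected, that probability is below 10⁻¹⁵ in both comparisons.

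**4. Exact power and size.** These sum the binomial probabilities of every table in which the test rejects. Chi-squared has no continuity correction. Two-sided Fisher adds the probabilities of all tables, with the margins fixed, that are no more likely than the one observed.

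| Scenario | Chi-squared | Fisher |
|---|---|---|
| Power, 150/150, 77.5% v 62% | 83.8% | 80.6% |
| Power, 150/150, 78% v 62% | 86.2% | 83.4% |
| Power, 120/120 (assumed), 78% v 62% | 77.7% | 73.5% |
| Power, 90/90 (assumed), 78% v 62% | 65.4% | 59.5% |
| Power, 150/75, 78% v assumed 50% | 98.8% | 98.5% |
| Power, 150/75, 78% v assumed 60% | 80.2% | 77.9% |
| Power, 150/75, 78% v assumed 62% | 71.2% | 68.3% |
| Size, 150/150, common rate 62% or 70% | 5.0% | 3.8% |

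**5. Results that reverse.** 109/150 v 93/150: χ² = 3.88, p = 0.049; Fisher p = 0.065. For combination v fluocinolone at an assumed 120/60, 92/120 v 37/60: χ² = 4.43, p = 0.035; Fisher p = 0.053.

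**The case against.** The strongest reply is that this is an obvious drafting slip with little consequence. An exception that always swallows its rule cannot have been intended, and SAP 4.7.1 and Protocol 10.1.10.1 both show that chi-squared was meant. Fisher is a valid test and conservative here, so a false positive becomes less likely, and the rate differences and confidence intervals are reported under either test. The stated 150 per arm matches the continuity-corrected formula, which approximates Fisher, and Fisher keeps 80.6% power at 77.5% v 62%. The larger losses at 120 and 90 per arm rest on assumed sizes, and most of the shortfall there comes from the smaller sample. The reversals are chosen borderline tables.

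All of that stands as a limit on the size of the effect. Two further limits also stand. For tables larger than 2x2, such as the ear pain scale categories, chi-squared is kept once at least 80% of expected counts are below 5, not only when all are. And time to end of ear pain, the principal secondary endpoint, uses a log-rank test and is unaffected.

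What does not stand is relying on presumed intent. The same wording appears in two SAP sections, and the literal text and the presumed intent give different p-values for a confirmatory endpoint. Nor is the protocol uniform: its synopsis assigns an age-stratified log-rank test to therapeutic cure, which leaves the SAP as the document that has to settle the method.

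**Conclusion.** The concern holds. For the primary endpoint, and for every secondary endpoint reduced to two levels and tested the same way, the written rule selects Fisher at any realistic sample size. It keeps chi-squared only where every expected count is too small for it. That conclusion needs no assumption beyond the 2x2 table and the planned arm sizes.

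The cost is moderate: about 3 points of power at 150 per arm (2.9 at 78% v 62%, 3.2 at 77.5% v 62%), and a true size of 3.8% in place of 5.0%. If the MITT-PA/SA population is smaller than planned, the loss grows to 4.2 points at an assumed 120 per arm and 5.9 at an assumed 90. Type I error is not inflated. The main harm is that the plan contradicts its own named primary test and leaves two candidate p-values for a borderline result, in a trial that must succeed in both comparisons.

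**What to change.** In SAP 4.7.2 and SAP 4.5.3, replace the condition with: *Fisher's exact test will be used if more than 20% of the expected counts are below 5, or if any outcome category is empty in a treatment group.* At the planned sizes this restores the chi-squared test named in Protocol 10.1.10.1 and SAP 4.7.1, and the secondary endpoints follow by reference. Check that the table shells and programs apply the corrected direction.

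The cost is one sentence in two places, with no change to data collection or sample size. It must be done before unblinding; SAP 4.11 already requires changes to planned analyses to be final before database lock.

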4.7.3 Secondary Efficacy Variables

Time to End of Ear Pain

Ear pain will be defined as ending on the first day (morning or evening) on which there is no use of analgesics, the diary pain score is zero and the score remains at zero for all subsequent visits until the end of the study. This clinical efficacy variable from the patient's perspective is the assessment of pain as recorded in the patient diary.

Throughout the study, patient or caregiver should record ear pain severity twice daily (morning and evening prior to dosing) in the diary using a proper pain scale according to patient's age until the end of study:

- Patients younger than 7 years old will use the Face, Legs, Activity, Cry, Consolability (FLACC) scale (it will be assessed by parents or caregivers).
- Patients from 7 years old to 13 years old will record the pain using the Wong Baker Faces Pain Scale.

Effective Date: [REDACTED]

Related to: [REDACTED]

CONFIDENTIAL

Project Document Version No. 2.0

Project Document Effective Date: Date of last signature

Page 21 of 34

- And patients 13 years old and older will record the pain using a Visual Analog Scale (VAS) scale.

The patient diary information together with investigator assessment will be used to ascertain the time point (morning or evening) and date at which the ear pain in the evaluable ear ended without use of analgesics.

Time to end of ear pain is defined as the interval (in days) between first dose of study medication and the first day (morning or evening) on which the ear pain in the evaluable ear ended (pain was absent and remains absent until the end of the study without using analgesic). This time will be calculated on the basis of the patient diary entries using a proper pain scale according to patient's age.

If a patient experiences an end to ear pain in the evaluable ear, then the TEOP will be recorded as the length of time between the first dose of study treatment and the time point entered in the field:

TEOP= date and time point of end of ear pain – date and time point of first dose of study medication

- If ear pain in the evaluable ear continued to the end of the study, the TEOP will be recorded as the length of time between the time of the first dose of study medication and the last time point when a pain measurement was recorded. For statistical purposes, such observations will be considered “censored”.

TEOP= date and time point of last ear pain measurement – date and time of first dose of study medication

- In patients with treatment failure (including rescue medication with otic or systemic antibiotics), the TEOP will be censored at the maximum value (17 days).
- Patients who discontinue or are lost to follow up, and for whom the pain persisted at the time of the last observation, will be censored at maximum length (17 days) in those cases when the diary information is not available.

The null hypothesis is that there is no difference in time to end of pain between the combination and the components alone. The alternative hypothesis is that there is difference in time to end of pain between the combination and the components alone. The comparison will be made using the log-rank test stratified on age (6 months to <18 years versus ≥ 18 years). The p-value will be shown for each comparison between the combination and individual component. The median TEOP will be calculated using the Kaplan Meier method and will be presented with its 95% CI for each treatment group.

Kaplan Meier plots will also be shown by treatment group and strata.

Sensitivity analysis of “time to end of pain” will be performed by using the full information as assessed from patient diaries without regard for the patient’s need for analgesic therapy.

Sustained Microbiological Outcome

For any patient with a culture positive for a pathogen at Visit 1, bacteriological response at Visits 3 will be classified as Eradication, Presumed Eradication, Persistence, Presumed Persistence, Superinfection or Indeterminate and bacteriological response at Visit 4 will be classified as Eradication, Presumed Eradication, Persistence, Presumed Persistence, Recurrence, Superinfection, Reinfection or Indeterminate, as defined in Section 4.7.2.

The number and percentage of patients with each response will be summarized by visit and treatment group. The proportion of patients with sustained microbiological cure i.e. with a response of Eradication or Presumed Eradication at both Visit 3 and Visit 4 will be compared between the treatment groups by using the same chi-squared test as the primary efficacy endpoint.

If a patient took rescue medication prior to Visit 4, he/she will be considered to not have achieved sustained microbiological cure.

A by-patient listing of sustained microbiological outcome will be provided.

Overall Clinical Outcome

Overall Clinical Outcome is based on the TSSS, which is calculated by the sum of otalgia score + edema score + otorrhea score. Patients will be allocated to one of the following categories for Overall Clinical Outcome:

1. Clinical Cure: TSSS is 0
2. Clinical Improvement: TSSS is different than 0 but lower than the previous visit
3. Clinical Failure: TSSS does not meet the definitions of Clinical Cure or Clinical Improvement.
4. Indeterminate: Discontinued (for reasons other than Clinical Failure) or lost to follow-up

Overall clinical outcome will be summarized by treatment group and visit in terms of proportion in each category at each visit.

Responses will be categorized into two groups for analysis. Clinical improvement, Clinical Failure, and indeterminate will be collapsed into a single category: Clinical Failure. Overall clinical outcome will be analyzed using the same method as the primary efficacy endpoint. A Pearson’s Chi Squared test for independence will be used to test that there is no difference between the combined treatment and each individual component at Visits 3 and 4.

If a patient took rescue medication prior to Visit 3, the response will be considered a clinical failure at Visit 3. Similarly, if a patient took rescue medication prior to Visit 4, the response will be considered a clinical failure at Visit 4.

A by-patient listing of overall clinical outcome will be provided.

Microbiological Outcome

Microbiological Outcome is described in Section 4.7.2.

Microbiological outcome will be summarized by treatment group and visit in terms of proportion in each category at each visit.

If a patient took rescue medication prior to Visit 3, the response will be considered a failure at Visit 3. Similarly, if a patient took rescue medication prior to Visit 4, the response will be considered a failure at Visit 4.

Responses will be summarized in terms of a 3-level response. Responses of Eradication or Presumed Eradication will be categorized as favorable. Responses of Persistence, Presumed Persistence, Superinfection, Reinfection, and Recurrence will be categorized as unfavorable. Indeterminate responses will be categorized as indeterminate. The proportion of patients with a favorable response at Visit 3 and Visit 4 will be compared between the Ciprofloxacin plus Fluocinolone acetonide and the Fluocinolone acetonide and between Ciprofloxacin and Fluocinolone acetonide treatment groups by using the same chi-squared test as the primary efficacy endpoint.

Microbiological outcome will also be presented by pathogen (*P. aeruginosa*, *S. aureus*, *T. otitidis*, and Other). The per-pathogen microbiological outcome will be derived for each pathogen identified at baseline based on the following classification:

- Eradication: elimination of pathogen identified in Visit 1 culture evidenced by the absence of that pathogen in a subsequent culture
- Presumed Eradication: elimination of pathogen identified in Visit 1 culture evidenced by the absence of any purulent discharge from which to obtain a subsequent culture in patients whose signs and/or symptoms of infection has improved or resolved
- Persistence: continued presence of pathogen identified in Visit 1 culture evidenced by the isolation of that pathogen in a subsequent culture
- Presumed Persistence: continued presumed presence of pathogen identified in Visit 1 culture when; the isolation of that pathogen in a subsequent culture was not performed, or a culture result was not available, in a patient with persistent or worsening signs and/or symptoms of infection
- Recurrence: if there is a reappearance of a pathogen (originally isolated at Visit 1) at Visit 4 eradicated or presumably eradicated at Visit 3

- Indeterminate: if none of the above definitions are met and the outcome cannot be determined

Note that new pathogens identified after Visit 1 do not have a per-pathogen outcome, the presence of a new pathogen after Visit 1 will be included in the overall microbiological response only.

A by-patient listing of microbiological outcome will be provided.

Brighton Grading

Brighton grading will be assessed at Visits 1, 3 and 4. For consistency, the same individual should perform the assessments at all 3 visits, if possible. Brighton grading will be assessed as:

- Grade 0: Normal
- Grade I: Tympanic membrane seen. Canal erythematous
- Grade II: Debris in ear canal. Tympanic membrane often obscured by debris.
- Grade III: Edematous ear canal. Tympanic membrane obscured by edematous ear canal. No systemic illness.
- Grade IV: Edematous ear canal. Perichondritis (pinna cellulitis). Systemic illness.

The number and percentage of patients with each grade will be summarized by visit and treatment group.

Grades will also be summarized in terms of a 3-level and a 2-level response. For the 3-level response, the proportion of patients with a Brighton grading of “0” will be considered as Resolved. It will be considered as “Improved” at Visit 3 and Visit 4 if the grade is lower than the previous visit. Brighton grading will be considered as “Not Improved” otherwise. Furthermore if Brighton grading is considered “Not Improved” or “Improved” in the 3-level response then it will be identified as “Not Resolved” in the 2-level response. If it is considered “Resolved” in the 3-level response then it will also be considered “Resolved” in the 2-level response.

If a patient took rescue medication prior to Visit 3, the response will be considered not resolved at Visit 3. Similarly, if a patient took rescue medication prior to Visit 4, the response will be considered not resolved at Visit 4.

For Visits 3 and 4, the proportion of patients with a response of Resolved and Not Resolved will be compared between the treatment groups by using the same chi-squared test as the primary efficacy endpoint.

A by-patient listing of Brighton grading data will be provided.

Otalgia

Effective Date: [REDACTED]

Related to: [REDACTED]

CONFIDENTIAL

Project Document Version No. 2.0
Project Document Effective Date: Date of last signature
Page 25 of 34

Otalgia will be assessed by the Investigator at Visits 1, 3, and 4. Otalgia will be assessed as Severe, Moderate, Mild, or Absent as defined in Section 4.7.2.

The number and percentage of patients with each outcome (Severe, Moderate, Mild or Absent) will be summarized by visit and treatment group.

Assessments will also be summarized in terms of a 3-level and a 2-level response. For the 3-level response, pain will be considered resolved at Visits 3 and 4 if the pain is assessed as Absent. Pain will be considered as "Improved" at Visit 3 and Visit 4 if pain is assessed by the investigator as "Mild" and was assessed as "Severe" or "Moderate" at Visit 1 (Day 1) or if pain was assessed by the investigator as "Moderate" at Visit 3 or Visit 4 and was assessed as "Severe" at Visit 1. Pain will be considered as "Not Improved" otherwise. Furthermore if pain is considered "Not Improved" or "Improved" in the 3-level response then it will be identified as "Not Resolved" in the 2-level response. If pain is considered "Resolved" in the 3-level response then it will also be considered "Resolved" in the 2-level response.

If a patient took rescue medication prior to Visit 3, the response will be considered not resolved at Visit 3. Similarly, if a patient took rescue medication prior to Visit 4, the response will be considered not resolved at Visit 4.

For Visits 3 and 4, the proportion of patients with a response of Resolved and Not Resolved will be compared between the treatment groups by using the same Chi-squared test as the primary efficacy endpoint.

A by-patient listing of otalgia data will be provided.

Edema

Edema will be assessed by the Investigator at Visits 1, 3 and 4. Edema will be assessed as Severe, Moderate, Mild, or Absent as defined in Section 4.7.2.

The number and percentage of patients with each outcome (Severe, Moderate, Mild or Absent) will be summarized by visit and treatment group.

Assessments will also be summarized in terms of a 3-level and a 2-level response. For the 3-level response, edema will be considered resolved at Visits 3 and 4 if the eardrum edema is assessed as Absent. Edema will be considered as "Improved" at Visit 3 and Visit 4 if edema is assessed by the investigator as "Mild" and was assessed as "Severe" or "Moderate" at Visit 1 (Day 1) or if edema was assessed by the investigator as "Moderate" at Visit 3 or Visit 4 and was assessed as "Severe" at Visit 1. Edema will be considered as "Not Improved" otherwise. Furthermore, if edema is considered "Not Improved" or "Improved" in the 3-level response then it will be identified as "Not Resolved" in the 2-level response. If edema is considered "Resolved" in the 3-level response then it will also be considered "Resolved" in the 2-level response.

If a patient took rescue medication prior to Visit 3, the response will be considered not resolved at Visit 3. Similarly, if a patient took rescue medication prior to Visit 4, the response will be considered not resolved at Visit 4.

For Visits 3 and 4, the proportion of patients with a response of Resolved and Not Resolved will be compared between the treatment groups by using the same Chi-squared test as the primary efficacy endpoint.

A by-patient listing of edema data will be provided.

Otorrhea

Otorrhea will be assessed by the Investigator at Visits 1, 3 and 4. Otorrhea will be assessed as Severe, Moderate, Mild, or Absent as defined in Section 4.7.2.

The number and percentage of patients with each outcome (Severe, Moderate, Mild or Absent) will be summarized by visit and treatment group.

Assessments will also be summarized in terms of a 3-level and a 2-level response. For the 3-level response, otorrhea will be considered resolved at Visits 3 and 4 if the otorrhea is assessed as Absent. Otorrhea will be considered as "Improved" at Visit 3 and Visit 4 if otorrhea is assessed by the investigator as "Mild" and was assessed as "Severe" or "Moderate" at Visit 1 (Day 1) or if otorrhea was assessed by the investigator as "Moderate" at Visit 3 or Visit 4 and was assessed as "Severe" at Visit 1. Otorrhea will be considered as "Not Improved" otherwise. Furthermore if otorrhea is considered "Not Improved" or "Improved" in the 3-level response then it will be identified as "Not Resolved" in the 2-level response. If otorrhea is considered "Resolved" in the 3-level response then it will also be considered "Resolved" in the 2-level response.

If a patient took rescue medication prior to Visit 3, the response will be considered not resolved at Visit 3. Similarly, if a patient took rescue medication prior to Visit 4, the response will be considered not resolved at Visit 4.

For Visits 3 and 4, the proportion of patients with a response of Resolved and Not Resolved will be compared between the treatment groups by using the same Chi-squared test as the primary efficacy endpoint.

A by-patient listing of otorrhea data will be provided.

Ear Pain Scales

Ear pain scales will be assessed by the patient twice a day in the patient's Diary Card to calculate the TEOP. The ear pain scales assessed at Visit 3 and Visit 4 will be categorized as follows:

- Disappeared if there is no ear pain
- Improved if the response is better than the response at Visit 1
- No change if the response is the same as the response at Visit 1
- Worsened if the response is worse than the response at Visit 1
- Missing if there is no response

The number and percentage of patients with each outcome will be summarized by visit and treatment group for each pain scale and for all pain scaled combined. The proportion of patients with the responses will be compared between the treatment groups by using the same Chi-squared test as the primary efficacy endpoint.

